3 LIST OF ABBREVIATIONS AND DEFINITIONS OF TERMS

ADR	Adverse Drug Reaction(s)
AE	adverse event(s)
AESI	adverse event of special interest
AIC	Akaike Information Criteria
ATC	Anatomical Therapeutic Chemical
AUC _{inf}	Area Under the Plasma Concentration-Time Curve Extrapolated to Infinity
AUC _{last}	Area Under the Plasma Concentration-Time Curve up to the Last Measurable Drug Concentration
AUC _{tau}	Area Under the Plasma Concentration-Time Curve to the End of the Dosing Period
BA _{CFU}	Bactericidal Activity as Assessed by CFU
BA _{LAM}	Bactericidal Activity as Assessed by Sputum LAM Assay
BA _{TTP}	Bactericidal Activity as Assessed by TTP
BCI	Bayesian Credibility Interval
BID	Bis in Die (Latin for twice a day)
BP	Blood Pressure
bpm	Beats Per Minute
BT	Body Temperature
BW	Body Weight
CFU	Colony Forming Units
CI	Confidence Interval
C _{max}	Maximum Plasma Drug Concentration
C _{min}	Minimum Plasma Drug Concentration
CRO	Contract Research Organization
CV	Coefficient of Variation
DBP	Diastolic Blood Pressure
EBA	Early Bactericidal Activity
EWV	Early Withdrawal Visit

ECG	Electrocardiogram
eCRF	Electronic Case Report Form
HRZE	Isoniazid (H), Rifampicin (R), Pyrazinamide (Z), Ethambutol (E)
Gates MRI	Gates Medical Research Institute
HR	Heart Rate
IDMC	Independent Data Monitoring Committee
LAM	Lipoarabinomannan
LLOQ	Lower Limit of Quantification
MAR	Minimum angle of resolution
MIC	Minimum Inhibitory Concentration
min	Minute
mL	Milliliter
MGIT	Mycobacteria Growth Indicator Tube
mITT	Modified Intent-to-Treat
PD	Pharmacodynamics
PE	Physical Examination
PK	Pharmacokinetics
PP	Per Protocol
PT	Prothrombin Time
QD	Quaque Di (Latin for once a day)
QTcF	QT Corrected for HR Using Fridericia's Method
RR	Respiratory Rate
SAE	Serious Adverse Event(s)
SAP	Statistical Analysis Plan
SBP	Systolic Blood Pressure
SoA	Schedule of Activities
SoC	Standard of Care
SOC	System Organ Class

TB	Tuberculosis
TID	Ter in Die (Latin for three times a day)
T _{max}	Time to Maximum Plasma Drug Concentration
TNTC	Too numerous to count
TTP	Time to sputum culture Positivity
λ_z	Elimination Rate Constant

Approved

4 INTRODUCTION

The purpose of this statistical analysis plan (SAP) is to describe the framework of the statistical analyses, including the planned tables, listings and figures to assess the safety, early bactericidal activity (EBA) and pharmacokinetics (PK) of TBA-7371 in adult participants with rifampicin-sensitive pulmonary tuberculosis. The details in this SAP are based on Gates MRI-TBD03-201 protocol amendment 3 (Version 4) dated 07 July 2020 and Independent Data Monitoring Committee (IDMC) charter, version 1 dated 07 October 2019.

5 OBJECTIVES AND ENDPOINTS

5.1 Primary Objectives and Endpoints

The primary bactericidal activity objective of this study is to demonstrate the 14-day early bactericidal activity from screening (“0”) to day 14 (EBA 0-14) of 5 dose regimens of TBA-7371 monotherapy and Isoniazid[H], Rifampicin[R], Pyrazinamide[Z], Ethambutol[E] (HRZE) fixed dose combination, as assessed by colony forming unit (CFU) counts on solid media culture. The primary endpoint associated with this objective is the average change per day, from screening (“0”) to day 14 [BAcfu(0-14)] of the \log_{10} CFU/mL counts.

The primary safety objective of this study is to assess the severe/serious adverse event (AE) burden of 5 dose regimens of TBA-7371 monotherapy and HRZE over a 14-day treatment period. The primary endpoint associated with this objective is frequency of study participants who experienced one or more severe (\geq grade 3) and /or serious AEs from day 1 to through day 15.

Primary early bactericidal activity and safety objectives and associated endpoints are summarized in the [Table 1](#).

Table 1. Primary Objectives and Endpoint

Objectives	Endpoint
Early bactericidal activity	
Demonstrate the 14-day EBA from screening (“0”) to day 14 of 5 dose regimens of TBA-7371 monotherapy and HRZE as assessed by CFU counts on solid media culture.	Slope, i.e. average change per day, from screening (“0”) to day 14 [BAcfu(0-14)] of the \log_{10} CFU/mL counts.
Safety	
Assess the severe/serious AE burden of 5 dose regimens of TBA-7371 monotherapy and HRZE over a 14-day treatment period.	Frequency of study participants who experienced one or more severe (\geq grade 3) and /or serious AEs from Day 1 through Day 15.

5.2 Secondary Objectives and Endpoint

Secondary EBA, safety and pharmacokinetics/pharmacodynamics (PK/PD) objectives and associated endpoints are summarized in Table 2.

Table 2. Secondary Objectives and Endpoint

Objectives	Endpoint
Early bactericidal Activity	
Demonstrate the EBA of the first 2 days (screening [“0”] to day 2) and of the remaining 12 days (day 2 to day 14) of 5 dose regimens of TBA-7371 monotherapy and HRZE, as assessed by CFU counts on solid media culture	
 • Slope, i.e. average change per day, from Screening (Day 0) to Day 2 [BA_{CFU}(0-2)] of the log₁₀CFU/mL counts; • Slope from Day 2 to Day 14 [BA_{CFU}(2-14)] of the log₁₀CFU/mL counts.
Demonstrate the EBA of 5 dose regimens of TBA-7371 monotherapy and of HRZE, as assessed by alternative methods: 
 • Time to sputum culture positivity (TTP) in Mycobacteria Growth Indicator Tube (MGIT) culture • Sputum lipoarabinomannan (LAM) assay 	
TTP:
 
 • Slope of the time to TTP in the MGIT system from Screening (Day 0) to Day 14 [BA_{TTP}(0-14)], • Slope of the TTP in the MGIT system from Screening (Day 0) to Day 2 [BA_{TTP}(0-2)]; • Slope of the TTP in the MGIT system from Day 2 to Day 14 [BA_{TTP}(2-14)]; 
LAM:
 
 • Slope of the log concentration of sputum LAM from Screening (Day 0) to Day 14 [BA_{LAM}(0-14)]; • Slope of the log concentration of sputum LAM from Screening (Day 0) to Day 2 [BA_{LAM}(0-2)]; • Slope of the log concentration of sputum LAM from Day 2 to Day 14 [BA_{LAM}(2-14)].
Safety	
Assess the adverse event (AE) profile of each dose regimen of TBA-7371 and HRZE over the 14-day treatment period.	Frequency from Day 1 through Day 15 of participants with AE and frequency of AEs: overall, by system organ class (SOC) and preferred term; by seriousness, intensity (severity), expectedness and relatedness to study drug.
Assess the impact on eye symptoms, visual acuity and color vision of each dose regimen of TBA-737 and HRZE over the 14-day treatment period.	
From Day 1 through Day 15:
 
 • Frequency of participants with any new (vs. Screening) eye symptom in one or both eyes. • Mean and frequency distribution of duration of each eye symptom. • Mean and frequency distribution of percentage of days with any eye symptom and each of the eye symptoms.

Table 2. Secondary Objectives and Endpoint

	
 Mean/median changes in visual acuity score from Screening to lowest score during Days 1-15. Frequency of participants with any new color vision abnormalities (tritan, protan, deutan) in one or both eyes and degree of severity (mild, moderate, severe).
Assess the impact on heart rate (HR), blood pressure (BP) and electrocardiogram (ECG) profile of each dose regimen of TBA-7371 and of HRZE over the 14-day treatment period.	
From Day 1 through Day 15:
 
 Mean and frequency distribution of changes in heart rate (HR), systolic blood pressure (SBP) and diastolic blood pressure (DBP) as measured by the following 2 (BP) or 3 (HR) methods: 
 Manual HR, SBP and DBP from vital signs, after at least 1 minute in supine position (“manual, supine”); Manual HR, SBP and DBP from vital signs, after 2 (± 0.5) minutes in standing position (“manual, 2-minute standing”); HR from ECG, supine position (“ECG, supine”) Frequency of participants with $\geq 25\%$ increase in HR, decrease in SBP, decrease in DBP vs. baseline as measured with any of the methods described above. Mean and frequency distribution of percentage of days with $\geq 25\%$ increase in HR, decrease in SBP, decrease in DBP vs. baseline. 
Mean/median change from Screening through Day 15 in PR, RR, QRS, QT, and QTcF interval values from baseline ECG.

Assess whether there is tachyphylaxis over the 14-day treatment period for HR, SBP, DBP and eye symptoms	
 Mean change in HR, SBP, and DBP from Day 1 to Days 4, 7, 10, 14, and 15 for each of 2 BP and 3 HR measurement methods described above. Change in frequency of participants with eye symptoms (all, severe, serious) and change in worst visual acuity score and frequency of color vision abnormalities (tritan, protan, deutan) in one or both eyes and degree of severity (mild, moderate, and severe) from Day 1 to Days 4, 7, 10, 14, and 15.
Assess whether cardiovascular and/or ophthalmic adverse events persist or recur up to 4 weeks after discontinuation of treatment with TBA-7371.	
 Mean change in HR, SBP, and DBP from Baseline to Days 28 and 42 and from Day 14 to Days 28 and 42 as measured by the following 2 (BP) or 3 (HR) methods: 
 Manual HR, SBP and DBP from vital signs, after at least 10 minutes in supine position (“manual, supine”);

Table 2. Secondary Objectives and Endpoint

	
 Manual HR, SBP and DBP from vital signs, after 2 (± 0.5) minutes in standing position (“manual, 2-minute standing”); HR from ECG, supine position (“ECG, supine”) Change in frequency of participants with eye symptoms (all, severe, serious) and change in mean visual acuity score and frequency of color vision abnormalities (tritan, protan, deutan) in one or both eyes and degree of severity (mild, moderate, and severe) from Screening to Days 28 and 42 and from Days 1-15 (combined) to Days 28-42 (combined).
Assess whether there are meaningful changes in safety laboratory measurement	
For each blood/serum and urine parameter:
 
 Mean, median, highest and lowest value. Shift tables from Screening to Day 3, Day 7, Day 14, and Day 42.
Secondary, PK and PK/PD	
Evaluate the pharmacokinetics of TBA-7371 monotherapy over the 14-day treatment period.	TBA-7371 concentration profiles and PK parameters over the 14-day treatment interval: C_{max} , T_{max} , C_{last} , T_{last} , AUC_{inf} , $AUC_{1\text{ st}}$, AUC_{tau} , C_{min} , half-life, accumulation ratios.
Identify the lowest exposure to of TBA-7371 associated with maximal EBA effect.	Expected concentration associated with 90% of the maximal TBA-7371 EBA effect (EC_{90}).

5.3 Exploratory Objectives

Details of exploratory objectives will be included in separate operational and/or analysis plans. Results of exploratory objectives may be reported separately from the main clinical study report.

Exploratory objectives may include but are not limited to:

- Exploration of the correlation between EBA and biomarkers such as mycobacterial cell-free DNA, ribosomal RNA ratio assay, sputum and/or peripheral blood gene expression profiles and serum cytokines or other proteins, urine LAM, and bacterial genotypic evaluations for emergence of resistance;
- Testing of susceptibility to TBA-7371 [minimum inhibitory concentration (MIC)];
- Population PK modeling.

6 STUDY DESIGN CONSIDERATIONS

6.1 Study Design

This is an interventional, 5-cohort, 3-step dose escalation clinical trial in adult participants between 18 to 60 years of age with rifampicin-sensitive pulmonary tuberculosis (TB). The escalation will occur sequentially in 3 steps: from Cohort I to Cohorts II and III, from Cohorts II and III to Cohort IV and from Cohort IV to Cohort V (see [Figure 1](#)). Within the 1st escalation step, participants will be randomized equally (1:1) to Cohort II or Cohort III, which have the same total daily dose (200 mg, see below). Within each cohort, participants will be randomized unequally (5:1) to TBA-7371 or HRZE (isoniazid [H] / rifampicin [R] / pyrazinamide [Z] / ethambutol [E]) fixed dose combination tablets. Rifafour® e-275 (Sanofi) tablets, a commercial presentation of HRZE approved and available in South Africa, will be used in the study. The study is open-label with masked laboratory assessments (except PK).

Each participant will undergo 3 study phases: Screening Phase, lasting up to 7 days, with no TB treatment; a 14-day Study Treatment Phase on TBA-7371 or HRZE; and a 28-day Follow-up Phase on standard of care TB treatment.

An IDMC will make dose escalation recommendations to the Sponsor. After the last Cohort I participant completing the Study Treatment Phase (day 14), the IDMC will recommend whether Cohort II and Cohort III can start enrollment (1st escalation step). The same approach will be taken for the 2nd escalation step from Cohorts II & III to Cohort IV and for the 3rd escalation step from Cohort IV to Cohort V. For each escalation step, the “go / no-go” recommendation will be based on accumulating safety data provided in an un-masked fashion to the IDMC. Additional data (e.g. PK) may be provided if available as supporting evidence.

Authorized study site personnel will dispense each dose of study drug.

This study will be open label for study participants, study site personnel, IDMC members, laboratory personnel involved in PK measurements and all sponsor and contract research organization (CRO) personnel. The study will be masked (blinded) for personnel involved in the conduct of all other laboratory procedures (including those for the primary end-point).

[figure not shown]
Study participants will be hospitalized for up to 7 days for the Screening Phase and will remain in hospital until the day after the last dose of study drug is dispensed (day 15). Written informed consent must be given before any screening procedure is started. Participants will leave the hospital on day 15 after all procedures scheduled for that day have been completed. Thereafter, participants will undergo scheduled visits on days 28 and 42 (± 3 days) as outpatients during the Follow-up Phase.

Candidates will be screened to achieve 90 randomized study participants. Within each dose escalation cohort, 18 participants will be randomly assigned in a 5:1 ratio to TBA-7371 (N=15) or HRZE (N=3). The total sample size of the HRZE group (all cohorts combined) will be 15, assuming all cohorts will be allowed to undergo treatment.

Within each cohort, there will be no replacement for the first 2 early withdrawals (drop-outs) occurring in the Treatment Phase. Drop-outs from the 3rd onwards will be replaced to ensure that the total number of participants completing study treatment in each cohort is at least 16. Participants who withdraw prematurely during the Follow-up Phase will not be replaced.

6.1.1 Study Schema

Figure 1. Study Schema

Schedule of activities is presented in Appendix 1.

6.2 Sample Size Determination

Anticipating all cohorts are to be assessed in the study, approximately 90 participants will be randomized in a 5:1 ratio to either TBA-7371 or control group, totaling N = 15 participants for each TBA-7371 treatment and control groups (receiving treatment with HRZE).

Bactericidal effect

Based on Diacon et al. (Diacon, 2013) standard deviations associated with BAcfu(0-14) were relatively consistent across 5 treatment groups, ranging from 0.05 to 0.08. If we assume conservatively that the true standard deviation of the BAcfu(0-14) measures for the TBA-7371 treatment groups is equal to 0.1, then with N = 15 per group we have 80% (90%) power to detect a true group mean BAcfu(0-14) reduction of 0.067 (0.079), using a 1-sided alpha = 5%. For reference, the observed BAcfu(0-14) reduction in Diacon et al, 2013 were 0.040, 0.056, 0.077, 0.104, and 0.122 for Bedaquiline 100 mg, 200 mg, 300 mg, 400 mg and standard HRZE, respectively.

Safety

With N = 15 per group, we have approximately 80% (90%) probability to observe at least one AE if the true AE rate is 10% (15%). We have only 54% probability to observe at least one AE if the true AE rate is 5%. Across the five TBA-7371 treatment groups (N=75), we have 90% probability to observe at least one AE if the true AE rate is 3.0%.

6.3 Efficacy Measures

Table 3. Efficacy Endpoint

	Endpoint
Primary EBA	Slope, i.e. average change per day, from Screening (Day 0) to Day 14 [$BA_{CFU}(0-14)$] of the log CFU counts.
Secondary EBA	
 • Slope, i.e. average change per day from Screening (Day 0) to Day 2 [$BA_{CFU}(0-2)$] of the log CFU counts. • Slope, i.e. average change per day from Day 2 to Day 14 [$BA_{CFU}(2-14)$] of the log CFU counts. • Slope of the time to sputum culture positivity (TPP) in the MGIT system from Screening (“0”) to Day 14 [$BA_{TPP}(0-14)$]. • Slope of the TPP in the MGIT system from Screening (Day 0) to Day 2 [$BA_{TPP}(0-2)$]. • Slope of the TPP in the MGIT system from Day 2 to Day 14 [$BA_{TPP}(2-14)$]. • Slope of the log concentration of sputum LAM from Screening (Day 0) to Day 14 [$BA_{LAM}(0-14)$] • Slope of the log concentration of sputum LAM from Screening (Day 0) to Day 2 [$BA_{LAM}(0-2)$] • Slope of the log concentration of sputum LAM from Day 2 to Day 14 [$BA_{LAM}(2-14)$].

6.4 Safety Measures

Table 4. Safety Endpoint

	Endpoint
Primary safety	Frequency of study participants who experienced one or more severe (\geq grade 3) and/or serious AEs from Day 1 through Day 15.
Secondary safety	
Adverse events from Day 1 through Day 15:
 
 • Frequency from Day 1 through Day 15 of participants with AEs and frequency of AEs: overall, by system organ class and preferred term; by seriousness, severity, expectedness and relatedness to study drug. 
Eye symptoms from Day 1 through Day 15:

Table 4. Safety Endpoint

	
Frequency of participants with any new (vs. Screening) eye symptom in one or both eyes.Mean and frequency distribution of duration (hours) of each eye symptom.Mean and frequency distribution of percentage of days with any eye symptom and each of the eye symptoms.Mean/median change in visual acuity score from Screening to lowest score during Days 1-15.Frequency of participants with any new color vision abnormalities (tritan, protan, deutan) in one or both eyes and degree of severity (mild, moderate, severe). 
Heart rate (HR) and blood pressure (BP) from Day 1 through Day 15:
 
Mean and frequency distribution of changes in HR, SBP and DBP as measured by the following 2 (BP) or 3 (HR) methods:
Manual HR, SBP and DBP from vital signs, after at least 10 minutes in supine position (“manual, supine”);Manual HR, SBP and DBP from vital signs, after 2 (± 0.5) minutes in standing position (“manual, 2-min standing”);HR from ECG, supine position (“ECG, supine”)Frequency of participants with $\geq 25\%$ increase in HR, decrease in SBP, decrease in DBP vs. baseline as measured with any of the methods described above.Mean and frequency distribution of percentage of days with $\geq 25\%$ increase in HR, decrease in SBP, decrease in DBP vs. baseline.Mean/median change from screening through day 15 in RR, PR, QRS, QT, QTcF values from baseline ECG. 
Tachyphylaxis over the 14-day treatment period for HR, SBP, DBP and eye symptoms:
 
Mean change in HR, SBP and DBP from Baseline (Day 1, pre-dose) to Days 4, 7, 10, 14, and 15 for each of the 2 BP and 3 HR measurement methods described above.Change in frequency of participants with eye symptoms (all, severe, serious) and change in worst visual acuity score and frequency of color vision changes from Day 1 to Days 4, 7, 10, 14 and 15. 
Cardiovascular and/or ophthalmic AEs persistence or recurrence up to 4 weeks after discontinuation of treatment with TBA-7371:
 
Mean change in HR, SBP and DBP from Baseline (Day 1, pre-dose) to Days 28 and 42 and from Day 14 to Days 28 and 42 for each of the following measurement methods:
--	---

Table 4. Safety Endpoint

	
○ Manual HR, SBP and DBP from vital signs, after at least 10 minutes in supine position (“manual, supine”);○ Manual HR, SBP and DBP from vital signs, after 2 (± 0.5) minutes in standing position (“manual, 2-min standing”);○ HR from ECG, supine position (“ECG, supine”) 
● Change in frequency of participants with eye symptoms (all, severe, serious) and change in worst visual acuity score and frequency of color vision changes from Screening (Day 0) to Days 28 and 42 and from Days 1-15 (combined) to Days 28-42 (combined). 
Safety laboratory measurements:
 
● Mean, median and range of each blood/serum and urine safety parameter at screening, Days 3, 7, 14, and 42.● Shift tables of blood/serum and urine safety parameter from screening to Days 3, 7, 14 and 42.
--	---

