Assess the impact on heart rate, blood pressure and ECG profile of each dose regimen of TBA-7371 and of HRZE over the 14-day treatment period.	
From Day 1 through Day 15:
 
 Mean and frequency distribution of changes in HR, SBP and DBP as measured by the following 2 (BP) or 3 (HR) methods: 
 manual (vital signs), after at least 10 minutes in supine position (“manual, supine”); manual, after 2 (± 0.5) minutes in standing position (“manual, 2-min standing”); HR from ECG, supine position (“ECG, supine”) Frequency of participants with $\ge 25\%$ increase in HR, decrease in SBP, decrease in DBP vs. baseline as measured with any of the methods described above. Mean and frequency distribution of percentage of days with $\ge 25\%$ increase in HR, decrease in SBP, decrease in DBP vs. baseline. Mean/median change from screening through Day 15 in PR, RR, QRS, QT, QTcF values from baseline ECG.
Assess whether there is tachyphylaxis over the 14-day treatment period for HR, SBP, DBP and eye symptoms.	
 Mean change in HR, SBP and DBP from Day 1 to Days 4, 7, 10, 14 and 15 for each of the measurement methods described above. Change in frequency of participants with eye symptoms (all, severe, serious) and change in mean visual acuity score and frequency of color vision changes from Day 1 to Days 4, 7, 10, 14 and 15.
Assess whether cardiovascular and/or ophthalmic adverse events persist or recur up to 4 weeks after discontinuation of treatment with TBA-7371.	
 Mean change in HR, SBP and DBP from screening to Days 28 and 42 and from Day 14 to Days 28 and 42 for each of the measurement methods described above. Change in frequency of participants with eye symptoms (all, severe, serious) and change in mean visual acuity score and frequency of

Objectives	Endpoints
	color vision changes from screening to Days 28 and 42 and from Days 1-15 (combined) to Days 28-42 (combined).
Assess whether there are meaningful changes in safety laboratory measurement	For each blood/serum and urine parameter: 
 • Mean, median, highest and lowest value. • Shift tables from screening to Day 3, Day 7, Day 14 and Day 42.
Secondary, PK and PK/PD	

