9.2 Definitions

Screening EBA Measure: Average of the EBA measurements (i.e., log CFU, TTP in MGIT, and log concentration of sputum LAM) from the day -2 and day -1 overnight sputum samples of the screening phase will be used to determine the screening EBA measurement. If one of the overnight sputum samples is missing, the single non-missing sample will be directly used as the screening EBA measurement.

Baseline definition for other efficacy and safety variables: The last assessment made prior to the first administered dose of study intervention will be considered baseline for analysis purposes. Baseline values of ECG and vital signs are measured on Day 1 before the first dose of study medication is administered.

Day 1: Study day 1 is the day of first administration of TBA-7371 or HRZE. Positive study days will be counted forward from Day 1. Day -1 will be the date immediately preceding Day 1, and negative study days will be counted backward from Day 1.

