12.5 Vital Signs

12.5.1 Intraday Vital Signs Results

Intraday values of vital signs (HR, SBP, and DBP) measured while in supine and while in standing at predose, and 2.5h, 10.5h, and 16.5h after the time of 1st daily dose of study drug on Days 1, 4, 7, 10, and 14 and changes from predose taken on the same day will be summarized using descriptive statistics by treatment group. Line plots of mean of intraday HR, SBP, and DBP measured while in supine and while in standing by treatment group will be provided.

Potentially clinically important criteria of intraday changes from presdose in HR, SBP, and DBP while measured in supine and while in standing are defined as follows:

- $\geq 25\%$ increase in supine HR
- $\geq 25\%$ increase in standing HR
- $\geq 25\%$ decrease in supine SBP
- $\geq 25\%$ decrease in standing SBP
- $\geq 25\%$ decrease in supine DBP
- $\geq 25\%$ decrease in standing DBP

For each of the criteria, the frequency and proportion (expressed in percent) of participants who met the criterion at each time point will be provided by treatment group. For the by-time point summary, the denominator for the proportion is the number of participants in the treatment group with non-missing values at predose and the given post-predose time point taken on the same day.

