12.5.2 Daily Vital Signs Results

Daily values of vital signs (HR, SBP, and DBP) measured while in supine and while in standing at baseline (Day 1 predose), Days 2 (predose), 3, 4 (predose), 5, 6, 7 (predose), 8, 9, 10 (predose), 11, 12, 13, 14 (predose), 15, 28, and 42 and changes from baseline will be summarized by treatment group using descriptive statistics. Line plots of mean of daily HR, SBP, and DBP measured while in supine and while in standing by treatment group will be provided.

Potentially clinically important criteria for changes from baseline in HR, SBP, and DBP while measured in supine and while in standing are defined as follows:

- $\geq 25\%$ increase in supine HR

- $\geq 25\%$ increase in standing HR
- $\geq 25\%$ decrease in supine SBP
- $\geq 25\%$ decrease in standing SBP
- $\geq 25\%$ decrease in supine DBP
- $\geq 25\%$ decrease in standing DBP

For each of the criteria, the frequency and proportion (expressed in percent) of participants who met the criterion at each time point will be provided by treatment group. For the by-time point summary, the denominator for the proportion is the number of participants in the treatment group with non-missing values at baseline and the given post-baseline time point.

For each of the criteria, any day that a participant whose vital signs results met the criterion will be counted toward the number of days with the criterion met in the study for that individual. Number of days with the criterion met will be summarized by treatment group using descriptive statistics.

Additionally, categorical number of days with the criterion met will be summarized by treatment group as follows:

- 1-3 days
- 4-6 days
- 7-9 days
- 10-12 days
- 13-15 days
- ≥ 16 days

The summary will include the frequency and proportion (expressed in percent) of participants for each category. For computing proportions, the denominator will be the number of participants in the treatment group who met the respective criterion.

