12.6.2 Daily ECG Results

Values of ECG variables (HR, QRS duration, RR, PR, QT, and QTcF intervals) measured at baseline (Day 1 predose), Days 4 (predose), 7 (predose), 10 (predose), 14 (predose), 15, 28, and 42 and changes from baseline will be summarized using descriptive statistics by treatment group.

Potentially clinically important criteria for QTcF are defined as follows:

- Observed: 451 to 480, 481 to 500, and >500 msec
- Change from baseline: 31 to 60, and >60 msec

For each of the criteria, the frequency and proportion (expressed in percent) of participants who met the criterion at each time point will be provided by treatment group. For the by-time point summary, the denominator for the proportion is the number of participants in the treatment group with non-missing values at baseline and the given post-baseline time point.

Additionally, values of ECG variables for sex subgroup (female and male) will be summarized similarly as described above. Boxplots of daily values of QTcF by treatment group and sex will be provided.

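### The SAP's heart-rate and blood-pressure tachyphylaxis contrast starts from an untreated reading and, as tabulated, ends at trough, so by itself it cannot show whether the post-dose effect wanes

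*SAP*

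**What the plan says.** Tachyphylaxis of heart rate (HR), systolic and diastolic blood pressure over the 14 days is a named secondary objective. Protocol Section 2.3 gives the reason: HR and BP effects seemed to lessen with repeated dosing in the Phase 1 study.

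The endpoint is worded in more than one way:

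- Protocol 3.2, Table 6: "Mean change in HR, SBP and DBP from Day 1 to Days 4, 7, 10, 14 and 15". No time of day is given.
- SAP 5.2, Table 2: "Mean change in HR, SBP, and DBP from Day 1 to Days 4, 7, 10, 14, and 15 for each of 2 BP and 3" (the last number counts the heart-rate methods). Again no restriction to pre-dose.
- SAP 6.4, Table 4: "Mean change in HR, SBP and DBP from Baseline (Day 1, pre-dose) to Days 4, 7, 10, 14, and 15". The reference is now pre-dose; the time of day on the later days is not given.

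SAP 9.2 fixes what that reference is: "Baseline values of ECG and vital signs are measured on Day 1 before the first dose of study medication is administered".

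Two kinds of SAP table use these data. The by-day tables compute change from that baseline. Vital signs (12.5.2) are taken "at baseline (Day 1 predose), Days 2 (predose), 3, 4 (predose), 5, 6, 7 (predose), 8, 9, 10 (predose), 11, 12, 13, 14 (predose), 15," followed by the two follow-up visits; ECG variables including HR (12.6.2) are "measured at baseline (Day 1 predose), Days 4 (predose), 7 (predose), 10 (predose), 14 (predose), 15, 28, and 42 and changes from baseline". The intraday tables (12.5.1 for vital signs, 12.6.1 for ECG) cover pre-dose and 2.5, 10.5 and 16.5 hours after the first daily dose on Days 1, 4, 7, 10 and 14. They show the values, and in addition "changes from predose taken on the same day will be summarized using descriptive statistics by treatment group".

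Protocol 9.4.2.2 also plans a model-based posterior probability of change from Day 1 to Day 14 for HR and BP. The SAP has no counterpart for HR or BP, and SAP Section 8 declares no changes from the protocol.

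**The concern.** Tachyphylaxis means that the same dose produces a smaller response on later days than it did at first. Estimating it needs an on-drug response on Day 1 and an on-drug response at the same time after dosing later. The Table 4 reference is a reading taken before any drug. If the later readings are pre-dose as well, the Day 1 response does not enter the contrast at all, and what is left is the effect still present at trough. A result near zero would then be compatible with full waning, with no waning, or with an effect that simply wears off between doses. At stake is the prespecified answer to a secondary objective that bears on how the cardiovascular findings are read when regimens are chosen.

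**Working it through.** The plan ties no numerical figure to this endpoint, so there is none to reproduce. The check has two steps.

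**Step 1: when are the later-day readings taken?** Dosing times come from protocol 6.1.3: once daily at 0 h; BID at 0 and 12 h; TID at 0, 7 and 14 h. Hours from the last dose to the next morning's pre-dose reading:

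- QD: 24 − 0 = 24 h
- BID: 24 − 12 = 12 h
- TID: 24 − 14 = 10 h

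The pre-dose values in 12.5.2 and 12.6.2 are troughs in every regimen. Day 15 is read in the morning before standard-of-care medication, so it has no post-dose reading either.

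**Step 2: what does each contrast return?** Let B be the Day 1 pre-dose value, E1 and E14 the rise above B at 2.5 h on Days 1 and 14, and f the share of the effect still present at the Day 14 pre-dose reading.

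- Table 4 contrast as run in 12.5.2: (B + f·E14) − B = f·E14
- Same-day change in 12.5.1: E1 on Day 1 and (1 − f)·E14 on Day 14
- Matched post-dose contrast: (B + E14) − (B + E1) = E14 − E1

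E1 does not appear in the first expression. The documents give no HR effect size or half-life, so the following inputs are assumptions: E1 = 15 bpm; E14 = 15 (no waning) or 5 (waning); f = 0, 0.10 or 0.25.

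| Day 14 result (bpm) | f = 0 | f = 0.10 | f = 0.25 |
|---|---|---|---|
| Table 4 contrast, no waning | 0 | 1.5 | 3.75 |
| Table 4 contrast, waning | 0 | 0.5 | 1.25 |
| Same-day change, no waning (Day 1: 15) | 15 | 13.5 | 11.25 |
| Same-day change, waning (Day 1: 15) | 5 | 4.5 | 3.75 |
| Matched 2.5 h contrast, no waning | 0 | 0 | 0 |
| Matched 2.5 h contrast, waning | −10 | −10 | −10 |

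The gap between waning and no waning on the Table 4 contrast is f × (15 − 5) = 0, 1.0 or 2.5 bpm, against 10 bpm on the matched contrast. The two explanations are also not separable. A Table 4 value of 1.25 bpm fits E14 = 5 with f = 0.25, and equally E14 = 15 with f = 1.25/15 = 0.083.

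The same-day change does distinguish the two cases, but imperfectly: with f = 0.10 to 0.25 it falls from 15 to between 13.5 and 11.25 although nothing has waned.

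**The case against.** The best reply is that the SAP already reports what is needed. Sections 12.5.1 and 12.6.1 give post-dose values and same-day changes on Day 1 and on Days 4, 7, 10 and 14, by treatment group, with line plots of the vital-sign means. A fall from 15 to 5 bpm would be visible there. With complete data, the matched mean can even be assembled from the planned tables: Day 14 same-day change plus Day 14 pre-dose change from baseline, minus Day 1 same-day change. At f = 0.25 this gives 11.25 + 3.75 − 15 = 0 without waning and 3.75 + 1.25 − 15 = −10 with it. This part stands. A reader might infer from Table 4 that the objective goes unanswered; the documents do not support that.

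What the reply leaves open is that neither intraday section is named as the tachyphylaxis analysis, neither specifies a between-day contrast or an interval for one, and the one rule that is labelled tachyphylaxis in Table 4 points elsewhere.

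It is also fair to say that Table 4 states no clock time for the later days. The trough reading rests on linking it to 12.5.2 and 12.6.2, the sections that compute change from the Day 1 pre-dose baseline. The link is reasonable, but the SAP does not state it.

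Finally, the objective also covers eye symptoms. Those assessments are made 2.5 hours after the first daily dose on Day 1 and on the later treatment days, so that part already has an on-drug reference and is not affected.

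**Conclusion.** The point holds for the HR, SBP and DBP contrast as Table 4 defines it and 12.5.2 and 12.6.2 tabulate it: it reflects trough effect and cannot by itself show waning of the post-dose response. The SAP is also inconsistent with itself, since Table 2 and the protocol set the reference only as Day 1. Post-dose information is collected and summarised, so waning can be examined descriptively; what is missing is a prespecified contrast that measures it.

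The structural conclusion does not depend on any assumed effect, because the Day 1 response is absent from the contrast whatever its size. The bpm figures do depend on assumptions. A reader might infer one small fixed loss of signal for every arm, but the documents give neither half-life nor effect size. The gap scales with the share of effect left at trough, which should be larger for BID and TID (12 and 10 hours since the last dose) than for QD (24 hours).

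**What to change.** 1. Reconcile SAP Table 4 with Table 2 and the protocol.
2. Define the HR/SBP/DBP tachyphylaxis endpoint as the within-participant difference between the post-dose value on Days 4, 7, 10 and 14 and the value at the same time on Day 1. Use 2.5 hours as the main time, with 10.5 and 16.5 hours as supportive. Report means with 95% CIs for each treatment group. Include HRZE, so that a general drift over the hospital stay can be seen. The Day 1 pre-dose baseline cancels, so it does not matter whether raw values or changes from that baseline are used.
3. Keep change from Day 1 pre-dose, including Day 15, as a separate summary of trough or persistent effect.
4. Either restore the Day 1 to Day 14 posterior-probability analysis of protocol 9.4.2.2 for HR and BP, or list its removal in SAP Section 8. If it is restored, state the time point and the direction for BP: the protocol asks for a decrease, whereas waning of a BP fall would appear as a rise at matched times.

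The protocol's schedule already collects these readings on Days 1, 4, 7, 10 and 14, so the contrast and reconciliation need no new data, only SAP wording and one extra table. Restoring the model in item 4 would add programming; listing its removal would not.
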